12.4 Discontinued Subjects

Discontinued subjects withdraw, or are withdrawn from the study after signing informed consent and prior to completing all study visits. Subjects signing consent, but withdrawing or withdrawn prior to randomization will be considered discontinued due to screen failure and the failed entry criterion will be documented (refer to Section 10).

Subjects may discontinue study participation at any time and for any reason. Subjects may be discontinued from the study at any time if, in the medical opinion of the Principal Investigator or designated, qualified medical personnel, continued participation poses a health risk to the subject. Subject numbers from discontinued subjects will not be reissued. Discontinued subjects will not be replaced.

12.5 Clinical Study Termination

The Sponsor reserves the right to close the investigational site or terminate the study in its entirety at any time, for any reasonable cause. The Investigator may also terminate the study at his/her site for reasonable cause. Reasons for the closure of an investigational site or termination of a study may include:

- The Investigator fails to comply with the protocol or good clinical practice (GCP) guidelines.
- Safety concerns.
- Inadequate recruitment of subjects by the Investigator.

If the clinical study is prematurely terminated or suspended, the Sponsor will inform the Investigator and the regulatory authorities (where applicable) of the termination/suspension and the reason for the termination/suspension. The Investigator should promptly notify the IRB/IEC of the termination or suspension and of the reasons.

If the Sponsor terminates the study for safety reasons, the Sponsor will immediately notify the Investigator(s), and provide written instructions for study termination and applicable subject follow-up.

13 DEVICE DEFICIENCIES AND ADVERSE EVENTS

13.1 General Information

An AE is any untoward medical occurrence, unintended disease or injury, or untoward clinical signs (including abnormal laboratory findings) in subjects, users, or other persons, whether or not related to the investigational medical device (test article). Refer to the Section 4 (Glossary of Terms) for definitions of all categories of AEs and SAEs.

Figure 13-1 Categorization of All Adverse Events

[figure not shown]
[figure not shown]

Figure 13-2

Categorization of All Serious Adverse Events

***Device Deficiencies***

A device deficiency may or may not be associated with subject harm (ie, ADE or SADE); however, not all ADEs or SADEs are due to a device deficiency. The Investigator should determine the applicable category for the identified or suspect device deficiency and report any subject harm separately. For definitions of device deficiency, malfunction and use error, refer to Section 4.

- Laser defect
- Laser optic
- Unable to calibrate laser
- Suspect product contamination (patient interface)
- Lack of effectiveness

13.2 Monitoring for Adverse Events

At each visit, after the subject has had the opportunity to spontaneously mention any problems, the Investigator should inquire about AEs by asking the standard questions:

- "Have you had any health problems since your last study visit?"
- "Have there been any changes in the medicines you take since your last study visit?"

Changes in any protocol-specific parameters evaluated during the study are to be reviewed by the Investigator. Any untoward (unfavorable and unintended) change in a protocol-specific parameter that is clinically relevant, in the opinion of the Investigator, is to be reported as an AE. These clinically relevant changes will be reported regardless of causality.

13.3 Procedures for Recording and Reporting

AEs are collected from the time of informed consent. Any pre-existing medical conditions or signs/symptoms present in a subject prior to the start of the study (ie, before informed consent is signed) are not considered AEs in the study and should be recorded in the Medical History section of the eCRF.

For each recorded event, the ADEs and SAEs documentation must include: date of occurrence, severity, treatment (if applicable), outcome, and assessments of the seriousness and causality. In addition, the Investigator must document all device deficiencies reported or observed with test and control entries on the Device Deficiency eCRF. The site must submit all available information on ADEs, SAEs, and device deficiencies to the Study Sponsor immediately as follows:

- All SAEs must be reported immediately (within 24 hours) of the Investigator's or site's awareness.
- ADEs that do not meet seriousness criteria and device deficiencies must be reported within 10 calendar days of the Investigator's or site's awareness.
- A printed copy of the completed **Serious Adverse Event and Adverse Device Effect** and/or **Device Deficiency** eCRF must be included with product returns.
- Additional relevant information after initial reporting must be entered into the eCRF as soon as the data become available.
- Document any changes to concomitant medications on the appropriate eCRFs.
- Document all relevant information from Discharge Summary, Autopsy Report, Certificate of Death etc, if applicable, in the narrative section of the ADE (for related AEs) and SAE eCRF.

NOTE: Should the EDC system become non-operational, the site must complete the appropriate paper **Serious Adverse Event and Adverse Device Effect** and/or **Device Deficiency** form. The completed form is faxed or emailed to the Study Sponsor at - [REDACTED] according to the timelines outlined above; however, the reported information must be entered into the EDC system once it becomes operational.

Any AEs and device deficiencies for non-study marketed devices/products will be considered and processed as spontaneous (following the post-market vigilance procedures) and should be communicated to the device's/product's manufacturer as per local requirements.

Study Sponsor representatives may be contacted for any protocol related question and their contact information is provided in the MOP that accompanies this protocol.

Further, depending upon the nature of the AE or device deficiency being reported, the Study Sponsor may request copies of applicable portions of the subject's medical records. The Investigator must also report all AEs and device deficiencies that could have led to a SADE according to the requirements of regulatory authorities or IRB/IEC.

Intensity and Causality Assessments

Where appropriate, the Investigator must assess the intensity (severity) of the AE based on medical judgment with consideration of any subjective symptom(s), as defined below:

Intensity (Severity)

Mild	An AE is mild if the subject is aware of but can easily tolerate the sign or symptom.
Moderate	An AE is moderate if the sign or symptom results in discomfort/interference with the subject's usual activities.
Severe	An AE is severe if the sign or symptom is incapacitating and results in the subject's inability to work or engage in their usual activities.

For every AE in the study, the Investigator must assess the causality (Related or Not Related to the medical device or study procedure). An assessment of causality will also be performed by Study Sponsor utilizing the same definitions, as shown below:

Causality

Related	An AE classified as related may be either definitely related or possibly related where a direct cause and effect relationship with the medical device or study procedure has not been demonstrated but there is a reasonable possibility that the AE was caused by the medical device or study procedure.
Not Related	An AE classified as not related may either be definitely unrelated or simply unlikely to be related (ie, there are other more likely causes for the AE).

The Study Sponsor will assess the AEs and may upgrade the Investigator's assessment of seriousness and/or causality. The Study Sponsor will notify the Investigator of any AEs that are upgraded from non-serious to serious or from unrelated to related.

13.4 Return product analysis

Study Sponsor representatives and their contact information are provided in the MOP that accompanies this protocol.

Alcon products associated with device deficiencies and/or product related AEs should be returned/reported per manufacturer instructions and must include the Complaint # which will be provided by Study Sponsor after the case is entered in the Study Sponsor's Global Product Complaint Management System (GPCMS).

13.5 Protocol Masking Requirements

Masked information on the identity of the assigned medical device should not be disclosed to the observer during the study (see Section 7.2). The Study Sponsor must be informed of all cases in which unmasking of the observer occurs and of the circumstances involved.

13.6 Follow-Up of Subjects with Adverse Events

The Investigator is responsible for adequate and safe medical care of subjects during the study and for ensuring that appropriate medical care and relevant follow-up procedures are maintained after the study.

The Investigator should provide the Study Sponsor with any new safety information (which includes new AEs and changes to previously reported AEs) that may affect the safety evaluation of the device. For AEs that are unresolved/ongoing at time of subject exit from study, any additional information received at follow-up should be documented in the eCRFs up to study completion (ie, database lock).

All complaints received after this time period will be considered and processed as spontaneous (following the post-market vigilance procedures) and should be communicated to the medical device's manufacturer as per local requirements.

The Investigator should also report complaints on non-Alcon products directly to the manufacturer as per the manufacturer's instructions or local regulatory requirements.

13.7 Pregnancy in the Clinical Study

Pregnancy is not reportable as an AE; however, complications may be reportable and will be decided on a case- by-case basis. An Alcon form will be utilized to capture all pregnancy-related information until birth of the child.

14 DATA REVIEW AND HANDLING

14.1 Completion of Source Documents and Case Report Forms

The nature and location of all source documents must be identified to ensure that original data required to complete the eCRFs exist and are accessible for verification by the monitor. If electronic source records are maintained, these records will be reviewed for 21 Code of Federal Regulations (CFR) Part 11 compliance and the method of verification will be determined in advance of starting the study. Data reported on the eCRFs must be derived from source documentation and be consistent with source documentation, and any discrepancies must be explained in writing. At a minimum, source documentation must include the following information for each subject:

- Subject identification (name, sex)
- Documentation of subject eligibility
- Date of informed consent, and a copy of signed informed consent form
- Dates of visits
- Documentation that protocol-specific procedures were performed
- Results of study assessments, as required by the protocol
- Documentation of AEs and other safety parameters (as applicable)
- Records regarding medical histories and the use of concomitant therapies prior to and during the study
- Date of study completion and reason for early discontinuation (if applicable)

It is required that the author of each entry in the source documents be identifiable (eg, initials or signature and date). Any change or correction to data reported in the source must be dated, initialed, and explained if necessary. Changes must not obscure the original entry (ie, an audit trail must be maintained). Direct access to source documentation (medical records) must be allowed for the purpose of verifying that the data recorded on the eCRF are consistent with the original source data.

The EDC system is designated for data collection and should be completed by designated individuals only. Required examinations must be recorded on the eCRFs. All data reported must have corresponding entries in the source documents. The Investigator will review the reported data and certify that the eCRFs are accurate and complete as indicated by signature. Subject identifiers must not be recorded on the eCRFs beyond subject number, demographics information, and/or other study identifiers.

Deviations from this protocol, regulatory requirements, and GCP must be recorded in the study records. An explanation of the deviation should be included, as applicable. In addition, corrective and preventive action should be identified, implemented, and documented within the study records.

14.2 Data Review and Clarifications

Upon completion of the eCRFs, the data will be reviewed by Alcon study personnel for accuracy and completeness. If corrections and/or any additions to the data are deemed necessary, queries will be generated by Alcon data management or the site management (study monitor) team and forwarded to the investigative site. Designated staff at each site are expected to respond to data queries in a timely manner and ensure that the corrections and changes made to the data in the EDC system are reflected in the subjects' source documentation. In addition, prior to study start (first subject first visit) a plan for data validation will be completed by Alcon Clinical Data Management and agreed upon by members of the Clinical Trial Management (CTM) team.

Concomitant medications entered into the database will be coded using the current version of the WHO Drug Reference List. Medical history and AEs will be coded using the medical dictionary for regulatory activities (MedDRA) terminology.

Upon completion of the study and once the database is declared complete and accurate, the database will be locked and data will be available for data analysis. Any changes to the database after lock will be implemented upon agreement between Alcon's clinical trial management and biostatistics department, and will be completed following Alcon's procedures for changes to a database after database lock.

15 ANALYSIS PLAN

15.1 Subject Evaluability

All subjects who satisfy the inclusion and exclusion criteria, and who sign the informed consent form, will be considered evaluable.

15.2 Analysis Data Sets

The full analysis set (FAS) will contain all eyes that are randomized and for which an IOL is successfully implanted; all eyes in the FAS will be assigned to the treatment actually received for analysis purposes. The FAS will be the primary analysis set for all effectiveness summaries and analyses, as well as all baseline and study summaries.

The safety analysis set will contain all eyes for which LenSx is activated and laser cut is started for the test eyes and corneal incision is begun for the control eyes; all eyes in the safety analysis set will be assigned to the treatment actually received. The safety analysis set will be the primary analysis set for all summaries and analyses of safety data.

Assignment of study eyes to the appropriate analysis set(s) will be determined prior to database lock.

15.3 Demographics and Baseline Characteristics

Demographic and baseline characteristics will be summarized by treatment group and overall using frequency tables for qualitative variables and descriptive statistics for quantitative variables.

Relevant medical history (ocular and nonocular) and current medical conditions will be tabulated by system organ class (SOC) and preferred term (PT) of the MedDRA dictionary. Other relevant baseline information will be listed and summarized as appropriate with descriptive statistics.

15.4 Effectiveness Analyses

15.4.1 Primary Effectiveness

15.4.1.1 Statistical Hypotheses

The null and alternative hypotheses for the primary effectiveness analysis are:

$$H_0: p_c \leq p_s$$

$$H_1: p_c > p_s$$

where p_c and p_s are the percentage of eyes with manifest refraction SE within 0.5 D of predicted postoperative SE at 1 month in the CRS and standard manual technique arms respectively.

15.4.1.2 Analysis Methods

The primary effectiveness analysis will be analyzed using a one-sided McNemar's test at the $\alpha=0.05$ level.

15.4.2 Secondary Effectiveness

15.4.2.1 Statistical Hypotheses

The null and alternative hypotheses are the same for all secondary analysis and can be presented as:

[figure not shown]
$$H_0: \mu_c \geq \mu_s$$

$$H_1: \mu_c < \mu_s$$

where μ_c denotes the mean value in the CRS group and μ_s denotes the mean value in the standard manual technique group for each of the respective secondary endpoints.

15.4.2.2 Analysis Methods

Each of the null hypotheses will be tested using a paired *t*-test; the family-wise type-I-error of 5% will be controlled using the Hochberg testing procedure outlined in Section 15.6.

15.4.3.2 Analysis Methods

Continuous data will be presented using n, mean, standard deviation, median, minimum, and maximum values. Categorical data will be presented with the number and percent in each category. All other summaries will be outlined in the statistical analysis plan (SAP).

15.5 Handling of Missing Data

The FAS and safety analysis set will not include any imputed values. Although missing data will occur, the influence of missing data is expected to be minimal.

15.6 Multiplicity

In order to control the overall type I error rate, the secondary effectiveness hypotheses will only be tested if the primary effectiveness null hypothesis is rejected at the 5% significance level (one-sided).

If the null hypothesis of the primary effectiveness endpoint is rejected, then the secondary effectiveness endpoints will be tested using the Hochberg testing procedure (Hochberg 1988). The Hochberg procedure is a step-up method for multiple testing controlling for the type I error rate at the 5% significance level.

15.7 Safety Analysis

Adverse Events

All information obtained on AEs will be summarized for ocular and nonocular AEs separately.

The number and percentage of all ocular AEs, including for either eye, will be tabulated by treatment and preferred term. An eye with multiple ocular AEs of the same preferred term is only counted once toward the total of this preferred term. A listing of nonocular AEs will be provided.

Device Deficiencies

The number and percentage of all device deficiencies will be tabulated by treatment. A listing of all device deficiencies will also be provided.

Other Safety Assessments

All other safety assessments (IOP, slit-lamp examination and dilated fundus examination) will be summarized. Number and percentage will be presented for categorical variables and descriptive statistics for continuous variables.

15.8 Interim Analyses

An interim analysis for the purposes of sample size re-estimation will be performed when the first 200 subjects who are randomized and treated complete their assessment for the primary effectiveness endpoint at Month 1 (Visit 3A). Alcon staff not involved with the conduct of the trial will re-estimate the sample size based on the data from the first 200 subjects. These staff will provide the re-estimated sample size and the predicted conditional power of the final test statistic based on that sample size. If the conditional power of the study is < 50% for the largest allowable sample size (500 subjects), no additional sample size beyond the originally planned 300 subjects will be added, and termination of the study may be considered. Because additional sample size will not be added if the conditional power of the study is < 50% at the maximum allowable sample size, any effect of the sample size modification on the type 1 error should be minimal (Mehta 2011).

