### **1.4 Masking**

This is an observer masked study. Site personnel who perform the manifest refraction subjective assessment and visual acuity testing after randomization will remain masked to the procedure group until after the final DBL. The same masking restriction applies to the analysts who perform the interim analysis. Surgery assignment may be known to Alcon, Novartis, and other site personnel. However they will not reveal the surgery assignment to masked site personnel or masked interim analysis team at any time during the study.

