### 5.3.1 Primary Effectiveness endpoint

[figure not shown]
The primary effectiveness analysis will be analyzed using a one-sided McNemar's test at the 5% significance level. P-value for the difference in the population proportions will be estimated and presented.

[figure not shown]
The number and percentage of eyes with manifest refraction spherical equivalent  $\leq 0.5D$  of predicted post-operative spherical equivalent will be presented by surgery procedure and visit.

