## 5.6 Interim Analysis for Effectiveness

An interim analysis for the purposes of sample size re-estimation will be performed when the first 200 subjects who are randomized and treated complete their assessment for the primary effectiveness endpoint at Month 1 (Visit 3A). Alcon staff not involved with the conduct of the trial will re-estimate the sample size based on the data from the first 200 subjects. These staff will provide the re-estimated sample size and the predicted conditional power of the final test statistic based on that sample size.

If the conditional power of the study is  $< 50\%$  for the largest allowable sample size (500 subjects), no additional sample size beyond the originally planned 300 subjects will be added, and termination of the study may be considered. Because additional sample size will not be added if the conditional power of the study is  $< 50\%$  at the maximum allowable sample size, any effect of the sample size modification on the type I error should be minimal (Mehta, 2000).

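### SAP 1.4 masks the interim analysts to procedure group, yet they must give conditional power of a one-sided test for a 50% gate whose assumed effect is not stated

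*Protocol*

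**What the plan says.** **Who does the interim analysis.** Protocol 15.8 gives it to sponsor staff outside trial conduct: "Alcon staff not involved with the conduct of the trial will re-estimate the sample size based on the data from the first 200 subjects". SAP 5.6 assigns it in the same way and says what they must deliver: "These staff will provide the re-estimated sample size and the predicted conditional power of the final test statistic based on that sample size".

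**The gate.** "If the conditional power of the study is < 50% for the largest allowable sample size (500 subjects), no additional sample size" is added beyond the initial 300, and stopping the study may be considered (Protocol 15.8; SAP 5.6 agrees). Both documents then conclude from this that "any effect of the sample size modification on the type I error should be minimal".

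**The final test.** "The primary effectiveness analysis will be analyzed using a one-sided McNemar's test at the 5% significance level" (SAP 5.3.1). The alternative in SAP 5.2.1 is that CRS has the higher success rate.

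**Masking.** SAP 1.4 masks the site assessors of refraction and acuity to procedure group until after final database lock, and adds: "The same masking restriction applies to the analysts who perform the interim analysis". Of other sponsor and site personnel who may know the assignment, it says "they will not reveal the surgery assignment to masked site personnel or masked interim analysis team at any time during the study".

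**Re-sizing.** Protocol 15.9 and SAP 7 make the interim discordance proportion the driver, in blocks of 50 between 300 and 500. Protocol 15.10 and SAP 7 give the inputs of the initial calculation: Miettinen's approximation, 83% against 75%, one-sided 5%, 90% power and 10% dropout. They work it at 21% and 33% discordance.

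**The concern.** Total discordance can be counted without knowing which eye had which technique. Conditional power of a one-sided test cannot be computed that way, because it needs the sign of the difference between pairs where only the CRS eye succeeded and pairs where only the manual eye succeeded. Dummy arm codes would supply only the absolute difference. So the team that SAP 1.4 describes cannot produce the figure that SAP 5.6 and Protocol 15.8 ask of it.

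A second gap would remain even if that team were unmasked. Conditional power needs an assumed effect for the subjects still to come, and neither document says whether this is the planned 8 points, the observed trend or something else. Two analysts could reach different decisions from the same table.

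At stake is whether up to 200 subjects are added, whether stopping is considered, and whether the trial keeps about 90% power when discordance is high.

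**Working it through.** **1. The plan's own figures.** With d = 0.83 − 0.75 = 0.08 and discordance ψ, Miettinen's approximation is

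n = [1.645ψ + 1.282·√(ψ² − d²(3 + ψ)/4)]² / (ψd²).

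- ψ = 0.21 gives 266.4, so 267, as stated.
- ψ = 0.33 gives 432.05, so 433, as stated.

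**2. Conditional power at the cap.** Let b and c be the CRS-only and manual-only successes among 200 interim pairs, ψ = (b + c)/200, M the final number of pairs, and e the effect assumed for the remaining pairs. By normal approximation,

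CP = P(Z > [1.645·√(Mψ) − (b − c) − (M − 200)e] / √[(M − 200)(ψ − e²)]).

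Take 500 randomized less 10% loss, so M = 450, and 66 discordant pairs, so ψ = 0.33. Then 1.645·√148.5 = 20.05. The re-estimated size is 432.05/0.9 = 480, rounded up to 500, whichever arm leads.

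| Split (CRS-only / manual-only) | e | Numerator | Denominator | CP |
|---|---|---|---|---|
| 38 / 28 | 0.08 (planned) | 20.05 − 10 − 20 = −9.95 | 8.99 | 87% |
| 38 / 28 | 0.05 (trend) | 20.05 − 10 − 12.5 = −2.45 | 9.05 | 61% |
| 28 / 38 | 0.08 (planned) | 20.05 + 10 − 20 = 10.05 | 8.99 | 13% |
| 28 / 38 | −0.05 (trend) | 20.05 + 10 + 12.5 = 42.55 | 9.05 | about 0% |

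A masked analyst sees the same data in all four rows, but the gate passes in the first two and blocks in the last two.

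**3. What the unstated effect changes.** These figures come from exact enumeration over b and c at 200 pairs. The size is Miettinen's n at the observed discordance with d = 0.08 held, divided by 0.9, rounded up to a block of 50 and limited to 300–500. The gate is evaluated at 450 pairs, blocked trials continue to 300, and the final test uses 90% of the randomized subjects.

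| Discordance | Quantity | No gate | Planned-effect gate | Trend gate |
|---|---|---|---|---|
| 21% | Power, true 8 points | 91.4% | 91.4% | 90.7% |
| 21% | Type I error | 0.050 | 0.050 | 0.048 |
| 21% | Mean N, no effect | 330 | 320 | 304 |
| 33% | Power, true 8 points | 89.6% | 88.9% | 81.2% |
| 33% | Type I error | 0.050 | 0.048 | 0.039 |
| 33% | Mean N, no effect | 482 | 390 | 325 |

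**4. Sensitivity.** The 81.2% rests on assumptions that the documents do not fix. With no loss (gate at 500 pairs) it is about 85%, against about 92% for the planned-effect gate. With 10% loss and every blocked trial stopped, it is 77.8%.

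**The case against.** **The re-sizing rule can be inferred.** A reader might conclude that nothing says how the new size is found. The documents do not support that. They name discordance as the driver, give Miettinen's inputs, work the 33% case with the other assumptions unchanged, and set the blocks and range. Only a sentence linking that calculation to the interim is missing.

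**Type I error is not shown to be inflated.** A reader might infer that the statement in Protocol 15.8 that "any effect of the sample size modification on the type 1 error should be minimal" is wrong. If the size were chosen to reach 90% conditional power under the planned effect, type I error would be about 0.061 at 21% discordance and 0.056 at 33%. But the documents tie the size to discordance and compute conditional power from the size, not the reverse. On that reading type I error is about 0.050 or less with either gate effect, and the statement holds.

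**Masking does not always matter.** It changes the sample size only when the two labellings fall on opposite sides of the gate and the re-estimated size exceeds 300. With a true 8-point effect, that is about 43–45% of trials at 21% discordance and 82–99% at 33%. This limits how often the problem arises but does not make the rule workable.

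**Part of a firewall exists.** The staff are outside trial conduct, and blocks of 50 limit back-calculation. That stands, and it makes the repair easier. The protocol does not mask these staff, but its silence does not settle which text should give way.

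**Conclusion.** The point holds. SAP 1.4 cannot be followed together with SAP 5.6 and Protocol 15.8, because conditional power of a one-sided test needs the direction that the masking withholds. This follows from the text and depends on no numerical assumption.

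The effect used in the gate is also missing. That matters little at the planning discordance of 21% (under 1 point of power). At 33% it is worth about 8 points, 89% against 81%, for a design that aims at 90%. Those figures assume 10% loss, a normal-approximation conditional power, size set from discordance with 8 points held, and blocked trials continuing to 300. Over the loss and stopping assumptions tried, the trend-gate figure runs from about 78% to about 85%.

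The finding concerns operability and power, not type I error. It should be fixed before the interim analysis. The planned 267 and 433 and the cap of 500 are unaffected.

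**What to change.** Reconcile SAP 1.4 with Protocol 15.8 and SAP 5.6 in one of two ways.

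- **(a) Keep the gate.** Unmask the interim staff for that analysis only, and keep by-arm results and conditional power from the study team and sites. Name the effect used in the gate in 15.8 and SAP 5.6; which effect is the sponsor's choice. Add one sentence that the new size comes from Miettinen's formula at the observed discordance with the 8-point difference held, and not from conditional power. In 15.10 and SAP 7, report the resulting power and type I error with the loss and termination assumptions stated.
- **(b) Drop the gate.** Re-size on masked discordance alone, and leave SAP 1.4 as it is. Power is then about 91% at 21% discordance and 90% at 33%, with type I error about 0.050. The termination prompt tied to conditional power would go with the gate.

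The cost is wording only, with no change to the cap, visits or data collected. Option (a) needs a documented firewall and, with a trend gate, an open statement of about 81% power at 33% discordance. Option (b) costs subjects if there is no effect: at 33% discordance the mean size is about 482, against 390 with a planned-effect gate or 325 with a trend gate.
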